2. At the conclusion of the memory skills group program, interested participants will be re-contacted by study staff to be formally enrolled in the Memory-SuSTAIN study. The initial outcome assessment data (T1) will then be collected within three weeks of completion of the memory group program (completion is defined as minimum attendance of four out of the six total weekly group sessions). Randomisation (1:1:1) will occur once participants are formally enrolled in the study.

A flyer will also be distributed to memory group participants inviting expressions of interest.

Inclusion Criteria

Participants will satisfy the following criteria:

1. Adults (age at least 18 years);
2. Primary diagnosis of stroke as determined by medical records;
3. At least 3 months post-stroke;
4. Everyday memory complaints, reported by self or other;
5. Sufficient cognitive and English language skills to participate in a memory skills group;
6. Completion of a memory skills group program at any of the participating clinical sites (defined as attending at least 4 of the 6 memory group sessions);
7. Access to a computer with a webcam and internet connection; and

8. Access to either SMS text messaging via a mobile phone with active service, or an active email service.

Exclusion Criteria

1. Severe psychiatric illness
2. Known presence of a neurodegenerative conditions (e.g. dementia), severe mental health conditions, or other known neurological disorder impacting cognition
3. Major illness and unlikely to survive up to final follow-up assessment
4. Current participation in other individual rehabilitation sessions focusing on memory or other cognitive functions.

Consent

Eligible participants will be provided with a verbal explanation of the study requirements and a participant information statement. Participants will be required to provide written consent before enrolment to the study. Consent forms will be stored securely at La Trobe University in individual client paper files (please see Data Handling and Security section below). The Participant Information and Consent Form (see attachment) will explain the following:

- What information is being collected
- Voluntary participation and withdrawal rights
- The purposes for which the information is being collected
- The period for which the records relating to the participant will be kept
- The form in which the data will be stored (i.e. whether identifiable or not)

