- The steps taken to ensure confidentiality and secure storage of data
- How privacy and confidentiality will be protected in any publication of the information
- The fact that the individual may access that information
- Any risks and benefits from participation

Group Randomisation and Blinding

[figure not shown]
Participants will be randomised into one of three groups:

- 1) Receiving 3 x 1-hour booster sessions over a period of 6 weeks
- 2) Receiving a minimum of 6 x SMS/email strategy reminders over a period of 6 weeks

3) No active maintenance.

The randomisation sequence will be generated by the Research Officer using Stata Version 15 (StataCorp, 2017). The sequence will be generated using random block sizes with 6 allocations per block (2 per condition), stratified by health service site to ensure equal distribution across sites. The randomisation schedule will then be uploaded to REDCap, which will ensure allocation concealment. As participants complete their post-break assessment (i.e. the T2/12-week outcome assessment, see flowchart below), the Memory-SuSTAIN study Research Officer will trigger randomisation within REDCap and inform both participants and the relevant team members delivering the maintenance interventions (i.e. those arranging SMS/Email reminders or conducting booster sessions) of the participant allocations.

PARTICIPANT FLOWCHART

MAINTENANCE INTERVENTION

Participants will be contacted following the 12-week assessment by the Memory-SuSTAIN research officer and informed of their random group allocation.

Maintenance Program option 1: Telehealth booster sessions

Participants in the Booster Sessions condition will receive three fortnightly sessions of one-hour duration each, with a trained clinician. Sessions comprise:

- Checking the progress of rehabilitation goals (previously negotiated with memory group clinicians);
- Reviewing and consolidating key compensatory and lifestyle strategies covered during the memory group program;
- Expanding the number and range of everyday situations to which these memory strategies could be applied; and
- Addressing any barriers to ongoing implementation of strategies.

Booster sessions will occur remotely via videoconferencing using Zoom, a freely available software program facilitating Internet-enabled videoconferencing. Booster sessions will also be video recorded and treatment fidelity checks conducted by an independent expert.

Maintenance Program option 2: SMS/Email Reminders

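### The Research Officer both writes the randomisation list and triggers each allocation, so the REDCap upload does not secure concealment against that role; the block rule also contradicts itself

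*Protocol*

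**What the plan says.** All references are to the Protocol.

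- **Generation** (Group Randomisation and Blinding): "The randomisation sequence will be generated by the Research Officer using Stata Version 15 (StataCorp, 2017".
- **Block rule** (same section): "The sequence will be generated using random block sizes with 6 allocations per block (2 per condition), stratified by health service site".
- **Concealment** (same section): "The randomisation schedule will then be uploaded to REDCap, which will ensure allocation concealment".
- **Operation** (same section): "the Memory-SuSTAIN study Research Officer will trigger randomisation within REDCap and inform both participants and the relevant team members" who deliver the interventions.
- **Timing** (same section): allocation is triggered "As participants complete their post-break assessment (i.e. the T2/12-week outcome assessment, see flowchart below". The Maintenance Intervention section agrees, since participants learn their group after the 12-week assessment. The Recruitment Procedure section instead says "Randomisation (1:1:1) will occur once participants are formally enrolled in the study".
- **Enrolment** (Recruitment Procedure): at the end of the memory group, "interested participants will be re-contacted by study staff to be formally enrolled in the Memory-SuSTAIN study". Which roles count as study staff is not stated.
- **Assessment** (Memory Skills Group Sites): the T1 to T4 assessments are done by an independent assessor who is masked to allocation.

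**The concern.** Allocation concealment means that nobody who can influence who enters, or in what order, knows the next assignment. Separating the person who makes the list from the person who uses it is the usual way to achieve this. Here one role does both, and the only safeguard named is a system into which that role loads its own list.

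Two things are at stake. The first is the composition of the arms: the Hypotheses section expects booster sessions to do best, then reminders, then no maintenance, so any steering in that direction would favour the expected result. The second is what is carried forward: the trial's procedures are themselves under test in Aim 2, and its results are meant to set the parameters of a Phase III trial.

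The block sentence is a separate, smaller defect. It cannot be programmed as written, because it describes both varying and constant blocks.

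**Working it through.** **1. Who knows what, and who can act on it.**

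- Research Officer: writes the list, triggers each allocation and announces it. Nothing in the Protocol restricts this role's copy of the list or its rights in REDCap. Concealment is not secured.
- Participants, site staff and assessors: given no access to the list. Concealment may hold.
- Intervention staff: told allocations after the event, with no stated control over who is triggered next.

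**2. What foreknowledge could change.** Under either timing statement, enrolment comes before allocation. If the Research Officer does not enrol, knowing the list cannot alter who is in the trial. Two routes remain.

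- *Order or timing of triggering.* The list is stratified by site and allocations are taken in sequence. If two people at one site are waiting, whoever is triggered first takes the next slot. No order is prescribed. Participants come from six-week groups run at each site, so several may reach T2 close together. That is an inference; the Protocol gives no group sizes.
- *Enrolment.* The term study staff neither names nor excludes the Research Officer.

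**3. Timing conflict.** Recruitment Procedure places randomisation at formal enrolment, which that section puts before T1 (the 6-week assessment). Group Randomisation and Blinding places it at T2 (the 12-week assessment). The nominal gap is 12 − 6 = 6 weeks. The T2 version keeps allocation well clear of enrolment; the other version brings the two together.

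**4. The block rule.** The stated figure reproduces: 3 arms × 2 per arm = 6. With 2 per condition in every block, the only possible size is 6. That is one fixed size, disclosed in the Protocol.

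**5. How sensitive the arms are.** There are 45 participants, 15 per arm. Suppose two people who differ by D on the final outcome are swapped between two arms. One arm mean rises by D/15 and the other falls by D/15, so the contrast moves by 2D/15 = 0.13D. If D is assumed to be 0.5 to 1 SD, one swap moves the contrast by 0.07 to 0.13 SD. This shows how sensitive small arms are. It does not predict that any swap will occur.

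**The case against.** The defence has real substance, and much of it stands.

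- **A reader might infer that there is no allocation concealment at all.** The document does not support that. REDCap can still hide the list from everyone except its author.
- **A reader might infer that the officer will steer participants.** Nothing shows intent. The Protocol ties the trigger to completion of T2, not to the officer's discretion. T2 is done by an independent assessor, so the officer is not shown to see T2 performance. Steering would need several same-site participants waiting at once, knowledge about them, and deliberate re-ordering. REDCap's audit trails (described under Option 2) could make re-ordering partly traceable.
- **A reader might measure the problem by how guessable blocks of six are.** For a complete 2:2:2 block, the best guess is right 1/3 + 2/5 + 1/2 + 8/15 + 3/5 + 1 = 101/30 = 3.37 times in 6 (56%), and on average 1.2 of 6 allocations (20%) are certain. Those figures describe someone who sees past allocations but lacks the list; the role that triggers allocation wrote the list. They also assume complete blocks. With equal recruitment assumed, 45/5 = 9 per site, and the guess rate is (101/30 + 37/30)/9 = 51%, with 1.2/9 = 13% certain. Neither pair measures this problem.
- **A reader might say that the bias could never be corrected.** That is too absolute. T1 and T2 are measured before allocation under the T2 timing, so imbalance on those measures is visible and can be adjusted for. Unmeasured differences would remain.
- **The trial is a pilot with a feasibility objective.** True, and it lowers the stakes for Aim 3. It does not make the statement about concealment correct.

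Masked assessors are no answer here: masking protects measurement, not the make-up of the arms.

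**Conclusion.** The point holds in a limited form. The Protocol asserts that the upload ensures concealment, and the procedure it describes does not deliver this for the Research Officer. For that role all 45 allocations could be known beforehand, provided the list is kept and consulted; this is a capability, not a documented use. The practical exposure is the order or timing of triggering within a site, plus enrolment if the officer takes part in it. The first rests on the inference that same-site participants reach T2 together, and the second on an undefined role.

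The contradiction in the block rule, and the conflict over when randomisation occurs, rest on the text alone and need no assumption. No size of bias can be derived from the document, and none is claimed. All of this should be put right before the first participant is randomised, because the remedy is cheap then and unavailable later.

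**What to change.** 1. Have an existing team member with no role in enrolment, participant contact or allocation generate and upload the list. The Research Officer only triggers, with no copy of the list and no REDCap rights to view it. The group that hosts REDCap is one possible source, but the Protocol does not say that it offers this.
2. Replace the block sentence with varying block sizes in multiples of three, held in a restricted file and not disclosed to recruiting or allocating staff. This removes known block ends but does not lower the average guess rate. In a simulation of nine allocations at one site, guessing the arm least used so far was right 51% of the time with fixed sixes and 53% with sizes 3, 6 and 9 mixed equally. Item 1 is therefore the main repair. Blocks of three are the easiest to guess, so larger multiples are preferable, at the price of looser balance within a small site.
3. Trigger same-site participants who are waiting together in a preset order, such as study ID.
4. Reconcile Recruitment Procedure (randomise once enrolled) with Group Randomisation and Blinding (randomise after T2), and state which roles enrol.

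The cost is a small amount of an existing person's time and a few sentences of Protocol wording. No change to sample size, visits or analysis is needed.

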 - b. The number of available and eligible potential participants and rates of recruitment

- c. The willingness of participants to be randomised
 - d. The appropriateness of the proposed set of outcome measures
 - e. Rates of adherence and compliance to follow-up assessments
 - f. The time required to collect and analyse data
3. Provide an initial estimate of the extent to which the two eHealth interventions maintain benefits from memory rehabilitation compared with no active maintenance, measured over an 18-week period; and
 4. Estimate the potential cost and cost-effectiveness of delivering the proposed maintenance intervention program (i.e. booster sessions and SMS reminders) compared with no active maintenance.

Ultimately, we will use the information from all four of these aims to estimate the parameters for a Phase III trial.

Hypotheses

We hypothesise that the level of everyday memory function at the end of the study, from largest to smallest effect, will be: eHealth booster sessions > SMS/Email reminders > no active maintenance.

STUDY DESIGN

Research Design

We will conduct a multi-site, single-blind, Phase II pilot randomised controlled trial (RCT) with three arms to evaluate two eHealth interventions designed to sustain the effects of memory skills training (booster sessions delivered via videoconferencing, and SMS/email reminders) compared to no active maintenance. We will use an intention to treat method of analysis, as well evaluate the maintenance interventions as per protocol in terms of:

- 1) Feasibility;
- 2) Effectiveness in prolonging intervention-related gains; and
- 3) Estimated cost.

PARTICIPANTS

Recruitment Procedure

Potential participants will be identified from survivors of stroke enrolled to participate in a memory skills group program at one of the health service sites participating in the study (please see Study Sites section). These sites are already running, or are planning to run, memory skills groups as part of usual care.

Recruitment will follow a two-step process:

1. Prior to commencing the memory skills group program, willingness to participate in the Memory-SuSTAIN study will be established. Health service staff will obtain verbal consent for identified potential Memory-SuSTAIN participants to be contacted by study staff to discuss participation.

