- Frequency of technical issues (e.g., message send failures, internet dropouts during telehealth sessions).
- The time required to collect data.
- The feasibility of data collection related to costs will be assessed by accessing the amount of missing data and participants opting out of providing these data.

Measures for Aim 3 (*Determining an initial estimate of intervention effectiveness*):

1) Goal Attainment Scaling (GAS; Turner-Stokes, Williams, & Johnson, 2009)

GAS is a person-centred measure of rehabilitation progress commonly used with clinical populations, to define and assess attainment of therapy goals. Participants will be invited to nominate two problematic types of memory lapses in everyday activities, in which improvements would represent realistic participation goals.

2) Everyday Memory Questionnaire-Revised (EMQ-R; Royle & Lincoln, 2008)

Self-reported lapses in memory will be assessed using the Everyday Memory Questionnaire-Revised, a 13-item item scale measure of memory failures in everyday activities.

3) Strategy Use Checklist

A self-report Strategy Use Checklist will record participant use of external strategies (e.g., lists, smartphone applications) and internal strategies (e.g., mental rehearsal, face-name association) from “Daily” to “Not at all”.

4) Rivermead Behavioural Memory Test – Third edition (RBMT-3; Malec, Zweber, & Depompolo, 1990)

Everyday memory will be assessed via the RBMT, an ecologically valid measure of functional performance in everyday tasks. 14 subtests cover verbal, visual, recognition, recall, immediate, and delayed memory performance. Items include demonstrating recall of a route around a room, recalling the locations of objects in the room, and recognising a series of faces.

5) The Valued Living Questionnaire (VLQ; Wilson, Sandoz, Kitchens, & Roberts, 2010)

As a brief self-report measure of quality of life from a behavioural perspective, the VLQ captures the extent to which participants’ actions are consistent with their values or the areas during the previous week.

6) Community Integration Questionnaire (CIQ; Willer, Ottenbacher, & Coad, 1994)

The CIQ is a 15-item self-report measure of social role limitation and community participation. Items include “approximately how many times do you participate in leisure activities such as movies, sports, restaurants, etc”.

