Measures for Aim 4 (*Estimating and comparing the potential cost-effectiveness of booster sessions or SMS reminders compared with no active maintenance*):

- Resource use and costs will be captured to determine the feasibility of conducting an economic evaluation and providing preliminary data as part of this Phase II study.
- Participant-level data will be obtained using the Adapted Resource Use Questionnaire for Stroke (developed by CI [name]) and
- Program delivery costs for each intervention arm e.g. costs of staff time to do telehealth or setup SMS program, costs of equipment, SMS service costs, etc. Costs of data collection for research are not counted.

Memory Skills Group Sites

Prior to randomisation for this trial, participants will first complete a 6-week memory skills group program which will be facilitated by trained neuropsychologists at multiple sites:

1. Monash Health - Cranbourne Integrated Health Centre (the primary site)
2. Austin Health – Heidelberg Repatriation Centre
3. Barwon Health – McKellar Centre
4. Melbourne Health - Royal Melbourne Hospital
5. Western Health – Sunshine Hospital

*(*Note: additional sites may be added, including Epworth Hospital).*

Clinicians at all sites will have undergone comprehensive training in delivering the memory skills group program by [name] before the trial commences. This training includes didactic instruction, watching videos of a previous memory group sessions, and supervision based on video recordings of the first group they facilitate. All memory skills group sessions will be video recorded throughout the study period, for treatment fidelity checks of a random selection of sessions by an independent expert. Treatment fidelity monitoring will include measures of adherence (using a session content checklist) and competence (using the eNACT Group Facilitation Competency Checklist; Wong, Grace, Baker, & McMahon, in press).

The flowchart below shows the design and flow of participants through the trial, and the timing of baseline and outcome assessments. Baseline (pre-memory skills group intervention) assessment (T0) will be conducted by neuropsychologists at the health service site. This will be a brief assessment of the first three outcome measures for Aim 3 only: Goal Attainment Scaling, the EMQ-R, and the Strategy Use Checklist (as an indication of the extent of the gains

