- Pairwise comparisons and linear mixed models will be used to explore between-group differences at T3 and T4 in acceptability ratings. Qualitative data will be thematically analysed to extract themes relating to intervention acceptability from participant interviews, using Braun and Clarke's (2006) approach to thematic analysis.

Aim 2 (*Determining whether the trial design is feasible*)

- Descriptive statistics will be calculated for feasibility measures, including rates of recruitment, study completion, and technological issues.

Aim 3 (*Determining an initial estimate of intervention-effectiveness*):

- Pairwise comparisons and linear mixed models will be used to explore between-group differences at each time point in clinical outcomes. The effect size of each maintenance condition, defined as the magnitude of change from T1-T4, will be estimated with Cohen's *d* based on output from regression models.

Aim 4 (*Estimating and comparing costs of booster sessions, SMS/email reminders, and no active maintenance*):

- Resource use data will be converted to costs and the average costs per participant for each intervention arm described and compared. The costs of each program will be accounted for in the determination of total costs and the average cost per participant. The reference year for costs will be 2019. The net cost per participant achieving the maintenance outcome will be estimated against the control group as a measure of potential cost-effectiveness. Various sensitivity analyses will be performed. If effectiveness information is able to be used for health benefit modeling relative to costs, then these will also be described to inform the business case and budget needed for a larger, fully powered Phase III study.

REPORTING OF RESULTS

Study results will be prepared for publishing at the completion of data collection and analysis. Results will be reported according to guidelines outlined by the Consolidated Standards of Reporting Trials (CONSORT) extension for randomised pilot and feasibility trials checklist, and the Template for Interventional Description and Replication (TIDieR) Checklist for describing an intervention. A final report will also be prepared for The Stroke Foundation in compliance with funding requirements.

DATA SECURITY AND HANDLING

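### The Aim 3 effect size, change from T1 to T4, spans six untreated weeks and by itself cannot separate a kept gain from no gain or a regained one

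*Protocol*

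**What the plan says.** The third aim (Study Objectives, Aims) is to "Provide an initial estimate of the extent to which the two eHealth interventions maintain benefits from memory rehabilitation compared with no active maintenance", over an 18-week period.

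Under Statistical Analyses, Aim 3, arms are compared at each time point by pairwise comparisons and linear mixed models. The headline quantity is then fixed: "The effect size of each maintenance condition, defined as the magnitude of change from T1-T4", expressed as Cohen's d from regression output.

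The pre-group assessment T0 is described under Memory Skills Group Sites: "This will be a brief assessment of the first three outcome measures for Aim 3 only: Goal Attainment Scaling, the EMQ-R, and the Strategy Use". Its stated purpose is to serve "as an indication of the extent of the gains" made in the group. The other three Aim 3 measures (RBMT-3, VLQ and CIQ, listed under Measures for Aim 3) therefore have no T0. T1, T2, T3 and T4 fall at weeks 6, 12, 18 and 24.

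On timing, Group Randomisation and Blinding has randomisation triggered as each participant completes the T2 assessment. Maintenance Intervention has participants told their allocation after that visit, and No Active Maintenance names T2 to T3 as the intervention phase. Recruitment Procedure, step 2, instead places randomisation at formal enrolment after the group ends.

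**The concern.** Maintaining a benefit presupposes a benefit that is there when the maintenance programme starts. To see that, one needs the level before the group (T0) and the level just before treatment (T2). The defined effect size uses neither. It starts at T1, shortly after the group, and runs through six weeks in which no arm is treated.

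Loss of gain in those weeks is a foreseeable course. The protocol's own background reports that in the earlier trial of the memory group the improvement in subjective everyday memory did not last to follow-up.

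At stake is what a result may be called. The estimates are meant to supply parameters for a Phase III trial. An effect size that mixes untreated change with treated change, and that looks the same for a kept, an absent or a regained gain, is a poor input for that purpose.

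**Working it through.** No figure in the protocol has to be reproduced for this point. The sample-size statement (45 participants, d = 0.33) plays no part in it. The check is which visits enter the effect size and what that can distinguish.

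**1. Untreated share of the window.** T1–T4 runs 24 − 6 = 18 weeks, which matches the period named in Aim 3. Treatment starts after T2, so 12 − 6 = 6 of the 18 weeks, one third, precede it.

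**2. Outcomes with a pre-group value.** GAS, EMQ-R and the Strategy Use Checklist have T0. RBMT-3, VLQ and CIQ do not. That is 3 of 6.

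**3. What T1–T4 change can separate.** The mean paths below are illustrative, in SD units with higher meaning better. The values are assumed and do not come from the protocol.

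| Path | T0 | T1 | T2 | T3 | T4 | T1–T4 | T0–T1 | T0–T2 | T2–T4 |
|---|---|---|---|---|---|---|---|---|---|
| Gain, held | 0 | 0.5 | 0.5 | 0.5 | 0.5 | 0 | 0.5 | 0.5 | 0 |
| No gain, flat | 0.5 | 0.5 | 0.5 | 0.5 | 0.5 | 0 | 0 | 0 | 0 |
| Gain, lost by T2, regained | 0 | 0.5 | 0 | 0.5 | 0.5 | 0 | 0.5 | 0 | 0.5 |
| No gain, then new gain | 0 | 0 | 0 | 0.4 | 0.4 | 0.4 | 0 | 0 | 0.4 |
| Gain held, then further gain | 0 | 0.5 | 0.5 | 0.9 | 0.9 | 0.4 | 0.5 | 0.5 | 0.4 |

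The first three paths share a T1–T4 change of 0, and the last two share 0.4. With T0 and T2 in hand all five separate. In the third path a rise of 0.5 SD after T2 shows as no change on the protocol's definition.

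**4. What randomisation protects.** Write B for an intervention arm and C for the control arm. The between-arm contrast of T1–T4 changes is (B4 − B1) − (C4 − C1) = (B4 − C4) − (B1 − C1). Under randomisation B1 − C1 has expectation zero, so the contrast still targets the T4 difference in level. The change within one arm has no such protection: it carries the T1–T2 movement in full. The protocol's wording, an effect size of each maintenance condition, invites that within-arm reading.

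**5. Precision of the missing context.** If T0–T2 change were reported for the three T0 measures, the 95% half-width in SD units is t(0.975, n−1) × √(2(1−r)/n), where r is the T0–T2 correlation (assumed, no dropout).

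| r | n = 45 (pooled) | n = 15 (one arm) |
|---|---|---|
| 0.7 | 0.233 | 0.429 |
| 0.5 | 0.300 | 0.554 |
| 0.3 | 0.355 | 0.655 |

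Pooled over all arms, which is legitimate because T2 precedes treatment, the change is estimated to within about 0.23 to 0.36 SD. Within one arm of 15 it is too imprecise to decide how a result should be labelled.

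**The case against.** The strongest reply is that this is a feasibility pilot. Its primary objective is feasibility, Aim 3 asks only for an initial estimate against no active maintenance, and the hypothesis concerns the level of everyday memory at the end of the study. The primary objective speaks of maintaining levels reached after the group, and T1 is that level. The protocol also compares arms at each time point, and an analysis plan that is not shown could use T0. Much of this stands: the T3 and T4 comparisons and the end-level hypothesis need no T0. But an analysis plan would have to depart from the stated T1–T4 definition, and it could not supply T0 values that are never collected.

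Four stronger readings are tempting and are not supported:

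- A reader might infer that maintenance can never be told from absence of gain. That is strictly so only for RBMT-3, VLQ and CIQ. GAS, EMQ-R and the Strategy Use Checklist are measured at T0, T1 and T2, and the EMQ-R measures the self-reported everyday memory that the primary objective names.
- A reader might infer that entry is wrongly defined because it asks for attendance and no gain: "Completion of a memory skills group program at any of the participating clinical sites (defined as attending at least 4 of the 6 memory group". Unselected completers are a legitimate target population, and randomisation balances non-gainers in expectation.
- A reader might infer that someone who never improved and stays flat counts as a success. Aim 3 has no participant-level rule. Aim 4 mentions a maintenance outcome per participant but does not define it.
- A reader might infer that all six outcomes are claimed to show a sustained group gain. The protocol lists them as measures of effectiveness and makes no such claim for each.

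The reply also limits the remedy. T0 is taken by site neuropsychologists, and T1 to T4 by an independent masked assessor, so T0–T2 change mixes assessors and has no control group. T0 data reach the study only with consent to transfer (Data Security and Handling), so some may be missing.

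**Conclusion.** The point holds in a limited form. The T1–T4 definition includes 6 untreated weeks out of 18 and ignores both the T2 value taken just before treatment and the T0 value collected to show the group gain. By itself it does not separate a kept gain from no gain or a regained one. For 3 of 6 outcomes a group gain cannot be computed from the planned data.

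The randomised comparison is not invalid: a difference at T3 or T4 stands as a difference in level. What lacks support is reading it as maintained group benefit.

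The 6-week figure rests on treatment starting after T2, as Maintenance Intervention and No Active Maintenance state. How often gains are absent or lost by T2 cannot be known from the protocol, so no size is put on the resulting misreading.

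**What to change.** 1. Replace the T1–T4 effect size with the between-arm difference at T3 and at T4, adjusted for the T2 value, for all six outcomes. For GAS, EMQ-R and the Strategy Use Checklist add T0 as a covariate where available, and show the T2-only estimate beside it so that nobody is lost for want of T0. Align the 18-week wording of Aim 3: T2 to T4 is 24 − 12 = 12 weeks.
2. For those three measures, report pooled T0–T1 and T0–T2 change in all randomised participants with 95% confidence intervals, as context for reading a difference as maintenance. State that T0 and the later visits use different assessors. Do not make the label depend on the course of a single arm of 15.
3. Describe RBMT-3, VLQ and CIQ results as between-arm differences, not as maintained group benefit.
4. Reconcile Recruitment Procedure with Group Randomisation and Blinding on when randomisation occurs. Item 1 depends on this: T2 is a clean covariate only if it precedes randomisation, or at least precedes disclosure of allocation and any treatment.

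The cost is a change to the Aim 3 analysis text, one or two model degrees of freedom, and a maintenance claim limited to three measures. No visits, participants or instruments are added.
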